## **12.5 Interim Analysis**

As stated above, the study design is a two-stage design. In the first stage, 18 patients will be accrued. If there are 6 or fewer responses in these 18 patients, the study will be stopped. Otherwise, 8 additional patients will be accrued for a total of 26.

## **12.6 Reporting and Exclusions**

### **12.6.1 Evaluation of Toxicity**

All subjects will be evaluable for toxicity from the time of their first treatment with ClaSPD.

### **12.6.2 Evaluation of Response**

All subjects included in the study will be assessed for response to treatment if they have received at least one treatment dose.

## **13. Adverse Event Reporting Requirements**

Adverse event (AE) monitoring and reporting is a routine part of every clinical trial. The investigator will be required to provide appropriate information concerning any findings that suggest significant hazards, contraindications, side effects, or precautions pertinent to the safe use of the drug or device under investigation. Safety will be monitored by evaluation of adverse events reported by subjects or observed by investigators or research staff, as well as by other investigations such as clinical laboratory tests, x-rays, electrocardiographs, etc.

## **13.1 Adverse Event Definitions**

- *Adverse event (AE)*: Any untoward medical occurrence in a patient or clinical investigation subject administered a pharmaceutical product and which does not necessarily have to have a causal relationship with this treatment. An AE can therefore be any unfavorable and unintended sign (including an abnormal laboratory finding, for example), symptom, or disease temporally associated with the use of study treatment, whether or not considered related to the study treatment.
- *Life-threatening adverse event or life-threatening suspected adverse reaction*: An adverse event or suspected adverse reaction is considered "life-threatening" if, in the view of either the investigator or sponsor, its occurrence places the patient or subject at immediate risk of death. It does not include an adverse event or suspected adverse reaction that, had it occurred in a more severe form, might have caused death.
- *Treatment-emergent adverse event (TEAE)*: Any event that was not present prior to the initiation of study treatment or any event already present that worsens in either intensity or frequency following exposure to study treatment.
- *Serious adverse event (SAE)*: Any untoward medical occurrence that, at any dose,

results in death; is life threatening (ie, an event in which the patient was at risk of death at the time of the event; it does not refer to an event that hypothetically might have caused death if it were more severe); requires inpatient hospitalization or prolongation of existing hospitalization; results in persistent or significant disability/incapacity; or is a congenital anomaly/birth defect. Important medical events that may not result in death, be life-threatening, or require hospitalization may be considered serious when, based upon appropriate medical judgment, they may jeopardize the patient or subject and may require medical or surgical intervention to prevent one of the outcomes listed in this definition. Examples of such medical events include allergic bronchospasm requiring intensive treatment in an emergency room or at home, blood dyscrasias or convulsions that do not result in inpatient hospitalization, or the development of drug dependency or drug abuse.

- *Suspected adverse reaction:* Any adverse event for which there is a reasonable possibility that the drug caused the adverse event. For the purposes of IND safety reporting, "reasonable possibility" means there is evidence to suggest a causal relationship between the drug and the adverse event. Suspected adverse reaction implies a lesser degree of certainty about causality than adverse reaction, which means any adverse event caused by a drug.
- *Unexpected adverse event or unexpected suspected adverse reaction:* An adverse event or suspected adverse reaction is considered "unexpected" if it is not listed in the investigator brochure or is not listed at the specificity or severity that has been observed; or, if an investigator brochure is not required or available, is not consistent with the risk information described in the general investigational plan or elsewhere in the current application, as amended. For example, under this definition, hepatic necrosis would be unexpected (by virtue of greater severity) if the investigator brochure referred only to elevated hepatic enzymes or hepatitis. Similarly, cerebral thromboembolism and cerebral vasculitis would be unexpected (by virtue of greater specificity) if the investigator brochure listed only cerebral vascular accidents. "Unexpected," as used in this definition, also refers to adverse events or suspected adverse reactions that are mentioned in the investigator brochure as occurring with a class of drugs or as anticipated from the pharmacological properties of the drug, but are not but are not specifically mentioned as occurring with the particular drug under investigation.

### **13.1.1 Expected Adverse Events**

Please refer to the package insert included in the Appendix for each of the components of the study treatment (ClaSPd).

### **13.1.2 Adverse Event Characteristics and Related Attributions**

**CTCAE term (AE description) and grade:** The descriptions and grading scales found in the revised NCI Common Terminology Criteria for Adverse Events (CTCAE) version 5.0 will be utilized for AE reporting. A copy of the CTCAE version 5.0 can be downloaded from the CTEP web site (<http://ctep.cancer.gov>).

The severity of the AE will be graded by the Investigator according to the CTCAE Grading Scale, version 5.0. If NCI CTCAE grading does not exist for an AE, the severity

will be characterized as “mild,” “moderate,” “severe,” or “life-threatening (corresponding to Grades 1 to 4) according to the following definitions:

- Grade 1 (Mild) events are usually transient and do not interfere with the patient’s daily activities.
- Grade 2 (Moderate) events introduce a low level of inconvenience or concern to the patient and may interfere with daily activities.
- Grade 3 (Severe) events interrupt the patient’s usual daily activities.
- Grade 4 events are Life-threatening.

The term “severe” is used to describe the intensity of an AE; the event itself could be of relatively minor clinical significance (e.g., ‘severe’ headache). This is not the same as a “serious” AE.

**Causality of the AE:**

- Not related: The lack of a strong temporal relationship of the event to the study treatment makes a causal relationship not reasonably possible, or other drugs, therapeutic interventions, or underlying conditions provide a sufficient explanation.
- Related: The temporal relationship of the event to the study treatment makes a definitive relationship, and the event is more likely explained by exposure to the study treatment than by any other drugs, therapeutic interventions, or underlying conditions.

### **13.1.3 Recording of Adverse Events**

All AEs that begin or worsen after the patient has provided informed consent will be recorded on the AE eCRF, regardless of whether dosing with study drug has commenced. AE monitoring should be continued for at least 30 days following the last dose of study treatment (i.e., through 30 days following last dose or until resolution or through the end of the study for events considered related to study treatment by the Investigator). AEs (including laboratory abnormalities that constitute AEs) should be described using a diagnosis whenever possible, rather than individual underlying signs and symptoms. When a clear diagnosis cannot be identified, each sign or symptom should be recorded as a separate AE.

The Investigator should ask the patient non-leading questions to determine if AEs occur during the study. AEs may also be recorded when they are volunteered by the patient, or through physical examination, laboratory tests, or other clinical assessments.

An AE should be followed until its resolution or until it is judged to be permanent, and assessment should be made at each visit (or more frequently, if necessary) of any changes in severity of the event, the suspected relationship to the study treatment, the interventions required to treat the event, and the outcome.

Laboratory abnormalities that constitute an AE in their own right (i.e., are considered to be clinically significant, induce clinical signs or symptoms, require concomitant therapy, or require changes in study treatment), should be recorded on the Adverse Events eCRF.

Whenever possible, a diagnosis, rather than a symptom should be provided (e.g., anemia instead of low hemoglobin). Laboratory abnormalities that meet the criteria for an AE should be followed until they have returned to baseline (at screening) or an adequate explanation of the abnormality is identified. When an abnormal laboratory or test result corresponds to a sign/symptom of an already reported AE, it is not necessary to separately record the laboratory/test result as an additional event.

A laboratory abnormality that does not meet the definition of an AE should not be reported as an AE. A Grade 3 or 4 event (severe per NCI CTCAE version 5.0) does not automatically indicate an SAE unless it meets the definition of serious, as defined above, and/or as per Investigator's discretion. A laboratory abnormality that results in a dose being held or modified would, by definition, be an AE and must be recorded as such in the eCRFs.

#### **13.1.4 Reporting of AE to WCM IRB**

All AEs occurring on this study will be reported to the IRB according to the IRB policy, which can be accessed via the following link:  
[http://researchintegrity.weill.cornell.edu/forms\\_and\\_policies/forms/Immediate\\_Reportin](http://researchintegrity.weill.cornell.edu/forms_and_policies/forms/Immediate_Reportin)  
Policy.pdf.

#### **13.1.5 Reporting Events to Participants**

The investigator or co-investigator will inform each participant about AEs and SAEs, and study-related results on an individual level. In addition, incidental findings associated with study procedures will be disclosed at the earliest opportunity to the participant.

#### **13.1.6 Events of Special Interest**

All secondary primary malignancies will be captured and reported as an AE.

Suspected unexpected serious adverse reactions (SUSARs) are SAEs that are unexpected and judged by the Investigator or Karyopharm to be related to the study treatment administered. SUSARs will be collected and reported to the competent authorities and relevant ethics committees in accordance with the FDA's "Safety Reporting Requirements for Investigational New Drugs and Bioanalytical/Bioequivalence Studies" or as per national regulatory requirements in participating countries.

In the event that an overdose is associated with an SAE, the SAE report form must be submitted to the IRB and Karyopharm Pharmacovigilance within 24 hours of awareness.

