## **2.4 Risk/Benefit Assessment**

### **2.4.1 Known Potential Risks**

Measures will be taken to ensure the safety of the patients participating in this trial, including the use of stringent inclusion and exclusion criteria and close monitoring. If toxicities are encountered, adjustments will be made to the study treatment as detailed in the sections below. All adverse events (AEs) and serious adverse events (SAEs) will be recorded during the trial and for up to 30 days after the last dose of study treatment or until the initiation of another anticancer therapy, whichever occurs first.

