### **7.10.2 Duration of Response and Survival Follow Up**

Every three months ( $\pm$  14 days) for 12 months after the EoT visit, if feasible and clinically appropriate, the following assessments should be obtained for patients who have not progressed to assess durability of response:

- SPEP and serum protein immunofixation
- UPEP (24-hour urine) and urine protein immunofixation
- Serum FLC
- Quantitative Ig levels
- Bone marrow aspirate, as clinically indicated, to assess progression
- Re-assessment of plasmacytomas by physical examination (if detected by physical examination at Screening)
- Skeletal survey (imaging) for bone lesions, including tumor measurements as clinically indicated to document response, at frequency determined by the Investigator

If these procedures cannot be obtained, at a minimum, a telephone call will be made to the patient (or the patient's family) every 3 months to inquire about the patient's MM status, general health, and information on any antineoplastic therapies utilized since discontinuation of study treatment.

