#### **12.4.2 Analysis of Secondary Endpoints**

Safety analyses will be performed using data available from all patients who receive  $\geq 1$  dose of the study treatment. Adverse Events (AEs) will be coded using the Medical Dictionary for Regulatory Activities (MedDRA) dictionary and displayed in tables and listings using System/Organ/Class (SOC) and Preferred Term. Analyses of AEs will be performed for those events that are considered to be treatment emergent AEs (TEAEs), defined as any AE with onset or worsening of a pre-existing condition on or after the first administration of study medication through 30 days following last dose or any event considered drug-related by the Investigator through the end of the study. AEs with partial dates will be assessed using the available date information to determine if treatment-emergent; AEs with completely missing dates will be assumed to be treatment-emergent.

AEs will be summarized by patient incidence rates. In all tabulations, a patient may contribute only once to the count for a given AE preferred term. The number and percentage of patients with TEAEs will be summarized, as well as the number and percentage of patients with TEAEs assessed by the Investigator as at least possibly related to treatment. The number and percentage of patients with any Grade  $\geq 3$  TEAE will be tabulated in the same manner. In the event that a patient experiences repeated episodes of the same TEAE, the event with the highest severity and/or strongest causal relationship to study treatment will be used for purposes of tabulations. Serious AEs (SAEs) will also be tabulated. No formal hypothesis-testing analysis of AE incidence rates will be performed.

All AEs (treatment emergent and post-treatment) will be listed in patient data listings. Separate by-patient listings will be provided for the following: patient deaths, SAEs, and AEs leading to withdrawal.

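### Section 13.1.6 promises capture of every second primary malignancy, but sets no period or procedure, the AE windows conflict, and later cases may be missed or only listed

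*Combined protocol and SAP*

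**What the plan says.** **The commitment.** Section 13.1.6 states "All secondary primary malignancies will be captured and reported as an AE". It names no start, no end, no source of information and no table.

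**The recording windows.**
- Section 2.4.1 records AEs and SAEs "for up to 30 days after the last dose of study treatment or until the initiation of another anticancer therapy, whichever occurs first".
- Section 13.1.3 says "AE monitoring should be continued for at least 30 days following the last dose of study treatment", and extends this "or until resolution or through the end of the study for events considered related to study treatment by the Investigator".
- Section 13.4 records non-serious AEs for 7 days and SAEs for 30 days, counted from the patient's final day in the study, not from the last dose. Section 3.4 places completion after the last duration-of-response/survival assessment.

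**The follow-up contacts.** The 30-day assessment (Section 6.1.3.1) includes adverse events. The 3-monthly list (Section 6.1.3.2) does not. Section 7.10.2 addresses patients who have not progressed. Where the tests cannot be obtained, it asks by telephone about myeloma status, "general health, and information on any antineoplastic therapies utilized since discontinuation of study treatment". Table 2 footnote 5b asks about survival, myeloma status and antineoplastic therapies, and directs the call, where feasible, to patients whose disease is not progressing.

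**The analysis.** Section 12.4.2 counts an event as treatment-emergent "through 30 days following last dose or any event considered drug-related by the Investigator through the end of the study". It adds that "All AEs (treatment emergent and post-treatment) will be listed in patient data listings".

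**The concern.** Second primary malignancy is the one clinical diagnosis that Section 13.1.6 singles out for complete capture. Such a promise needs three things: a rule that tells the site to record the event whenever it occurs, a question that brings it to light, and a table that counts it. The plan leaves each of them open for the months after treatment.

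At stake is whether the reported count is complete. Under Section 13.1.3 and the TEAE definition, a malignancy found several months after the last dose is assured of recording and tabulation only if the investigator attributes it to study treatment. That is hard to judge for one patient in a single-arm trial whose participants have had two to four prior lines of therapy. Section 13.1.2 also sets a high bar: the only alternative to unrelated is an event explained better by study treatment than by any other drug or condition. Two sites following different sections could record the same late cancer differently. The primary endpoint and the two-stage decision rule are not affected.

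**Working it through.** There is no sample-size, power or alpha figure behind this point, so nothing of that kind needs reproducing. The check is a side-by-side reading, followed by a calculation of how much follow-up depends on which window applies.

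**1. What each section does with a malignancy diagnosed 6 months after last dose and judged unrelated**

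| Section | Consequence |
|---|---|
| 13.1.6 | Report as an AE; no time limit stated |
| 2.4.1 | Outside the recording period |
| 13.1.3 | Beyond the required minimum; not forbidden, not required |
| 13.4 read with 3.4 | Inside the recording period |
| 13.2.3 | If serious, not reported to the drug supplier without suspected causality |
| 12.4.2, TEAE table | Not counted |
| 12.4.2, listings | Listed, if it was recorded |

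**2. Whether anyone would ask**

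The 3-monthly contact has no AE item in Section 6.1.3.2, and neither description of the call names a new cancer. General health appears in Section 7.10.2 but not in footnote 5b. Both ask about antineoplastic therapy, which would bring up a cancer treated with drugs but not necessarily one treated by surgery alone. A patient who has progressed falls outside the group named in footnote 5b, although Section 7.10 follows subjects for 12 months or until death.

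**3. How much time is affected**

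Inputs: about 10 months of treatment and about 24 months on study (Section 1, Participant Duration); 12 months of follow-up after end of treatment (Section 7.10); a 30-day window, with a 7-day visit allowance (Sections 13.1.3 and 7.10.1). One month is taken as 30.44 days, and follow-up is counted from last dose.

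- Follow-up beyond the 30-day window: 12 − 30/30.44 = 11.0 months; 11.0/12 = 92%.
- With the 7-day allowance: 12 − 37/30.44 = 10.8 months; 10.8/12 = 90%.
- Share of participant time, taking 10 + 12 = 22 months: 11.0/22 = 50%.
- Share taking the stated 24 months: (24 − 10 − 30/30.44)/24 = 13.0/24 = 54%.
- Under Section 13.4 read with Section 3.4: recording runs past the last follow-up assessment, so the gap is 0.

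Footnote 5b gives 18 months of calls where Sections 6.1.3.2, 7.10 and 7.10.2 give 12. The figures above use 12.

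**The case against.** The strongest case on the other side is that the plan, read as a whole, does cover late malignancies.

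- **Section 13.4 extends recording through follow-up** when read with Section 3.4, and it has the investigator ask about AEs at each study visit. This stands as a qualification. However, it is a third window that does not agree with Sections 2.4.1 and 13.1.3. The plan does not say that the 3-monthly telephone contact counts as such a visit, and its item list has no AE entry.
- **Section 13.1.3 sets a minimum.** It says at least 30 days. A reader might infer that Sections 13.1.3 and 13.1.6 give opposite instructions. They do not: a floor for AEs in general is compatible with a specific rule that has no time limit. What is missing is a statement that the specific rule prevails.
- **Post-treatment AEs are listed.** A reader might infer that late malignancies go unreported. The documents do not support that, because a recorded event would appear in the listings. A by-patient listing may be adequate for one or two events, but it holds only what was recorded and has no denominator.
- **The calls are not silent.** General health and antineoplastic therapy could each bring a new cancer to light. The defect is the lack of an explicit question, and the restriction of the calls to patients who are not progressing.

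A reader might also want a number of missed events, for example by multiplying up to 26 × 11/12 = 23.8 person-years by an incidence rate. The documents give no rate. The product would also assume no deaths, full contact with all 26 patients, no case found through the existing calls, and that Section 13.4 does not apply.

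**Conclusion.** The point holds in a limited form. Section 13.1.6 makes a commitment without a period or a procedure, and the sections that would carry it out disagree. Malignancies arising more than 30 days after last dose may be missed. If judged unrelated, they would at most be listed and not tabulated. The affected time is about 11 of the 12 follow-up months, or 50% to 54% of participant time, if the 30-day window governs, and none if Section 13.4 governs; the plan does not say which. These shares rest on the protocol's own estimate of about 10 months of treatment and on full follow-up without deaths. The number of events at risk cannot be estimated from the documents. It would go too far to conclude that AE recording stops at 30 days in every case, or that late malignancies will go unreported. This is a gap in safety ascertainment and reporting that should be closed; it does not touch the efficacy analysis.

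**What to change.** 1. In Section 13.1.6, state that second primary malignancies are recorded from first dose to end of study regardless of causality.
2. Reconcile Sections 2.4.1, 13.1.3 and 13.4 with that rule, so that one AE window applies and the malignancy rule is a named exception where the general window is shorter.
3. Add any new cancer diagnosis to the existing 3-monthly contact in Section 7.10.2 and Table 2 footnote 5b, for all patients in follow-up, progressed or not. Reconcile the 12 and 18 months of calls at the same time.
4. In Section 12.4.2, leave the TEAE definition as it is and add a separate table of second primary malignancies giving the number of patients and the person-time at risk.

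The cost is protocol wording, one question per scheduled contact (with contacts extended to progressed patients still in follow-up) and one small table. Treatment does not change.

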#### **13.1.7 Reporting of Pregnancy**

Pregnancy per se is not considered to be an AE; however, it is discussed here because of the importance of reporting pregnancies that occur during studies and because a medical occurrence observed in the mother or fetus/newborn would be classified as an AE. To ensure patient safety, a pregnancy occurring while the patient is on study treatment must be reported to Karyopharm Pharmacovigilance by email or fax within 24 hours of first knowledge of its occurrence as well as to the Pomalidomide REMS

program.

The pregnancy should be followed up to determine outcome, including spontaneous or voluntary termination, details of the birth, and the presence or absence of any birth defects, congenital abnormalities, or maternal and/or newborn complications.

Pregnancies must be reported to Karyopharm, regardless of whether the patient received selinexor or other study drugs, regardless of whether the patient withdraws from the study or the study is completed, for 3 months after the patient receives his/her last dose of study treatment. Patients should be instructed to inform the Investigator regarding any pregnancies.

Any SAE that occurs during pregnancy must be recorded on the SAE report form (e.g., maternal serious complications, therapeutic abortion, ectopic pregnancy, stillbirth, neonatal death, congenital anomaly, birth defect) and reported within 24 hours in accordance with the procedure for reporting SAEs.

A pregnancy in a female partner of a male patient must be reported to Karyopharm and the Pomalyst REMS program within 24 hours of learning of its occurrence.

